7.3 LOST TO FOLLOW-UP

A participant will be considered lost to follow-up if the participant repeatedly fails to return for scheduled visits and is unable to be contacted by the study site.

The following actions must be taken if a participant fails to return to the clinic for a required study visit:

- The site must attempt to contact the participant and reschedule the missed visit as soon as possible, counsel the participant on the importance of maintaining the assigned visit schedule and ascertain whether or not the participant wishes to and/or should continue in the study.
- Before a participant is deemed lost to follow-up, the Investigator or designee must make every effort to regain contact with the participant. These contact attempts should be documented in the participant's medical record.

- Should the participant continue to be unreachable, the participant will be considered to have withdrawn from the study.

Discontinuation of sites or of study as a whole are handled as part of [Appendix 1](#).

8. STUDY ASSESSMENTS AND PROCEDURES

Study procedures and their timepoints are summarized in the SoA (Section 1.3). Prospective approval of protocol deviations, also known as protocol waivers or exemptions, is not permitted.

Immediate safety concerns should be discussed with the Sponsor immediately upon occurrence or awareness to determine if the participant should continue or discontinue study treatment.

Procedures conducted as part of the participant's routine clinical management (e.g., blood count) and obtained before signing of the ICF may be utilized for screening or baseline purposes provided the procedure met the protocol-specified criteria and was performed within the timeframe defined in the SoA.

Repeat or unscheduled samples may be taken for safety reasons or technical issues with the samples.

8.1 EFFICACY ASSESSMENTS

Efficacy assessments are not applicable for this study.

8.2 SAFETY ASSESSMENTS

Planned timepoints for all safety assessments are provided in the SoA (Section 1.3).

Safety assessments will consist of monitoring and recording AEs, including SAEs and AEs of special interest (AESI); measurement of protocol-specified safety laboratory assessments; measurement of protocol-specified vital signs, ECGs; and other protocol-specified tests that are deemed critical to the safety evaluation of the study.

8.2.1 Physical Examinations

A complete physical examination should be performed at screening and will include, at a minimum, assessments of the cardiovascular, respiratory, gastrointestinal, dermatological, neurological, and musculoskeletal systems in addition to the head, eyes, ears, nose, throat, neck, and lymph nodes. Height and weight will also be measured and recorded. Further examination of other body systems may be performed in case of evocative symptoms at the Investigator's discretion.

At subsequent visits (or as clinically indicated), symptom-directed physical examinations should be performed. Weight will also be measured and recorded according to SoA (Section 1.3).

Investigators should pay special attention to clinical signs related to previous serious illnesses.

Any abnormality identified at baseline should be recorded on the General Medical History and Baseline Conditions eCRF.

Changes from baseline abnormalities should be recorded in participant's notes. New or worsened clinically significant abnormalities should be recorded as AEs on the Adverse Event eCRF.

8.2.2 Vital Signs

Tympanic temperature, pulse rate, respiratory rate, and blood pressure will be assessed.

Blood pressure and pulse measurements will be assessed with a completely automated device. Manual techniques will be used only if an automated device is not available. When possible, the same arm should be used for all blood pressure measurements. The non-infusion arm should be used during infusion in the IV cohorts. Blood pressure and pulse measurements should be preceded by at least 5 minutes of rest for the participant in a quiet setting without distractions (e.g., television, radio, cellular phones, conversation).

Vital signs (to be taken before blood collection for laboratory tests) will be measured after 5 minutes of rest and include temperature, SBP and DBP, pulse rate, and respiratory rate. Three readings of blood pressure and pulse will be taken. The first reading should be rejected. The second and third readings should be averaged to give the measurement to be recorded in the eCRF.

8.2.3 Electrocardiograms

TriPLICATE 12-lead ECG recordings will be obtained at specified timepoints (see Section 1.3). Three interpretable ECG recordings (e.g., without artifacts) must be obtained at each specified timepoint (± 5 minutes). Single 12-lead ECG recordings may be obtained at unscheduled timepoints as indicated.

All ECG recordings must be performed on a device that is equipped with reliable, automated algorithms for measuring heart rate and ECG intervals and capable of local printing. Paper copies of ECG tracings will be kept as part of the patient's permanent study file at the site.

Lead placement should be as consistent as possible. ECG recordings should be performed after the patient has been resting in a supine or semi-supine position for at least 10 minutes, and the patient should remain in a supine or semi-supine position during recording. The same positioning should be maintained for each patient throughout the study. ECG recordings should be performed prior to other procedures scheduled at that same time (e.g., vital sign measurements, blood draws) and should not be performed within 2.5 hours after any meal. Circumstances that may induce changes in heart rate, including environmental distractions (e.g., television, radio, conversation), should be avoided during the pre-ECG resting period and during ECG recording.

Paper copies of all ECG tracings must be reviewed, annotated to indicate any clinical findings, signed, and dated by a medically qualified member of the site staff. For each timepoint, average heart rate, RR interval, PR interval, QRS interval, uncorrected QT interval, and QTcF based on machine readings of triplicate ECG tracings should be recorded on the appropriate eCRF. Any morphologic waveform changes or other ECG abnormalities must be documented on the eCRF.

If at a particular postdose timepoint the mean QTcF is >500 ms or >60 ms longer than the baseline value (i.e., last value prior to initiation of study treatment), another ECG must be recorded, ideally within the next 5 minutes, and ECGs should be repeated at least hourly until two successive ECGs show resolution of the findings. A PK sample should be obtained if not already scheduled for that timepoint.

8.2.4 Clinical Safety Laboratory Assessments

Normal ranges for the study laboratory parameters must be supplied to the Sponsor before the study starts. A list of clinical laboratory tests to be performed is provided in [Appendix 4](#), and these assessments must be conducted in accordance with the local laboratories process. If analysis is required to be done centrally, the samples and assays should be clearly identified, and instructions may be provided by the central laboratory manual according to the requirements from the SoA (Section [1.3](#)).

The Investigator must review the laboratory report, document this review, and record any clinically relevant changes occurring during the study in the AE section of the eCRF. The laboratory reports must be filed with the source documents. Clinically significant abnormal laboratory findings are those which are not associated with the underlying disease, unless judged by the Investigator to be more severe than expected for the participant's condition.

- In the event of unexplained abnormal clinically significant laboratory test values, the tests should be repeated immediately and followed up until they have returned to the normal range and/or an adequate explanation of the abnormality is found.
- If such values do not return to normal/baseline within a period judged reasonable by the Investigator, the etiology should be identified and the Sponsor notified.
- If laboratory values from non-protocol-specified laboratory assessments performed at the local laboratory require a change in participant management or are considered clinically significant by the Investigator (e.g., SAE, AE, or dose modification), then the results must be recorded in the eCRF.

Results of clinical laboratory testing will be recorded on the eCRF or received as electronically produced laboratory reports submitted directly from the local or central laboratory.

Additional blood or urine samples may be taken at the discretion of the Investigator if the results of any test fall outside the reference ranges or clinical symptoms necessitate additional testing to monitor participant safety.

Where the clinical significance of abnormal laboratory results at screening is considered uncertain, screening laboratory tests may be repeated before enrollment to confirm eligibility.

If there is an alternative explanation for a positive urine or blood test for drugs of abuse (e.g., previous occasional intake of a medication or food containing, e.g., codeine, benzodiazepines, or opiates), the test could be repeated to confirm washout.

On the basis of continuous analysis of the data in this study and other studies, any sample type not considered to be critical for safety may be stopped at any time if the data from the samples collected do not produce useful information.

8.2.5 Medical History and Demographic Data

Medical history includes clinically significant diseases, surgeries, reproductive status, smoking history, and use of alcohol and drugs of abuse, and all medications (e.g., prescription drugs, OTC drugs, herbal or homeopathic remedies, nutritional supplements) used by the participant prior to the screening visit (see Section 6.5).

Demographic data will include age, sex, and self-reported race/ethnicity. The information about race/ethnicity of CHB participants is important because host genetics may modulate responses to study treatments. In addition, the information can be used to infer the likely HBV genotype where genotype information has not been obtained in routine clinical care, which is a common circumstance. There are different HBV variants with geographical distribution ([Tanwar and Dusheiko 2012](#); [Sunbul 2014](#)) that show different transmission modalities (e.g., vertical, in childhood, in adulthood), disease course, and response to treatment. The relevance of HBV genotypes is that HBV genotypes have a distinct geographical distribution and are known to influence clinical and virological parameters to treatment responses to, for example, IFN ([Rajoriya et al. 2017](#)).

For the participants with CHB, the detailed HBV history will be documented, which will include date of HBV diagnosis, mode of HBV infection (if known), HBV genotype (if documented), all previous HBV treatments and outcomes of treatments, occurrence of NUC resistance (if any), previous evaluations of cirrhosis, and dates/outcomes of liver biopsies (if any).

8.3 ADVERSE EVENTS AND SERIOUS ADVERSE EVENTS

The definitions of an AE or SAE can be found in [Appendix 2](#). AESI and disease-related events and/or disease-related outcomes not qualifying as AEs or SAEs are discussed in Section 8.3.6.

The Investigator and any qualified designees are responsible for ensuring that all AEs (including assessment of seriousness, severity, and causality; see [Appendix 2](#)) are recorded on the Adverse Event eCRF and reported to the Sponsor in accordance with instructions provided in this section and in [Appendix 2](#).

Procedures used for recording AEs are provided in [Appendix 3](#):

- Diagnosis versus signs and symptoms:
 - Infusion-/injection-related reactions
 - Other AEs
- AEs occurring secondary to other events
- Persistent or recurrent AEs
- Abnormal laboratory values
- Abnormal vital sign values
- Abnormal liver function tests
- Deaths
- Preexisting medical conditions
- Lack of efficacy or worsening of the condition being studied
- Hospitalization or prolonged hospitalization

8.3.1 Period and Frequency for Collecting Adverse Event and Serious Adverse Event Information

The method of recording, evaluating, and assessing causality of AEs and SAEs and the procedures for completing and transmitting SAE reports are provided in [Appendix 2](#).

Investigators will seek information on AEs at each participant's contact. All AEs, whether reported by the participant or noted by study personnel, will be recorded in the participant's medical record and on the Adverse Event eCRF as follows:

After informed consent has been obtained **but prior to initiation of study treatment**, only SAEs caused by a protocol-mandated intervention should be reported (e.g., SAEs related to invasive procedures such as biopsies). Any other AE should not be reported.

After initiation of study treatment, all AEs, regardless of relationship to study treatment, will be reported until the last scheduled follow-up visit.

Post-study AEs and SAEs: The Investigator is not required to actively monitor participants for AEs after the end of the AE reporting period, defined as their last scheduled follow-up visit.

However, if the Investigator learns of any SAE (including a death) or other AEs of concern that are believed to be related to prior treatment with study treatment at any

time after a participant has been discharged from the study, and the Investigator considers the event to be reasonably related to the study treatment or study participation, the Investigator must promptly notify the Sponsor. For the procedure of reporting, see [Appendix 2](#).

8.3.2 Method of Detecting Adverse Events and Serious Adverse Events

Care will be taken not to introduce bias when detecting AEs and/or SAEs. Open-ended and non-leading verbal questioning of the participant is the preferred method to inquire about AE occurrence.

A consistent methodology of non-directive questioning should be adopted for eliciting AE information at all participant evaluation timepoints.

8.3.3 Follow-Up of Adverse Events and Serious Adverse Events

8.3.3.1 Investigator Follow-Up

The Investigator should follow up on each AE until the event has resolved to baseline grade or better, the event is assessed as stable by the Investigator, the event is otherwise explained, the participant is lost to follow-up (Section [7.3](#)), or the participant withdraws consent. Every effort should be made to follow up on all SAEs considered to be related to study treatment or study-related procedures until a final outcome can be reported.

During the study period, resolution of AEs (with dates) should be documented on the Adverse Event eCRF and in the participant's medical record to facilitate source data verification. If, after follow-up, return-to-baseline status or stabilization cannot be established, an explanation should be recorded on the Adverse Event eCRF.

All pregnancies reported during the study should be followed up on until pregnancy outcome and reported according to the instructions provided in Section [8.3.5](#).

8.3.3.2 Sponsor Follow-Up

For SAEs, AESIs, and pregnancies, the Sponsor or a designee may follow up by telephone, fax, electronic mail, and/or a monitoring visit to obtain additional event details and outcome information (e.g., from hospital discharge summaries, consultant reports, and/or autopsy reports) to perform an independent medical assessment of the reported event.

8.3.4 Regulatory Reporting Requirements for Serious Adverse Events

Immediate notification by the Investigator to the Sponsor of an SAE (regardless of relationship to study treatment) is essential so that legal obligations and ethical responsibilities towards the safety of participants and the safety of a study treatment under clinical investigation are met.

The Sponsor has a legal responsibility to notify both the local regulatory authority and other regulatory agencies about the safety of a study treatment under clinical investigation. The Sponsor will comply with country-specific regulatory requirements relating to safety reporting to the regulatory authority, IRB/IEC, and Investigators.

Investigator safety reports must be prepared for suspected unexpected serious adverse reactions (SUSAR) according to local regulatory requirements and Sponsor policy and forwarded to Investigators as necessary.

An Investigator who receives an Investigator safety report describing an SAE or other specific safety information (e.g., summary or listing of SAEs) from the Sponsor will review and then file it along with the Investigator's Brochure and notify the IRB/IEC, if appropriate according to local requirements.

For immediate (i.e., no more than 24 hours after learning of the event) and expedited reporting requirements from Investigator to Sponsor and from Sponsor to Health Authority, Investigators, IRB and EC, see [Appendix 2](#), Section 5.

8.3.4.1 Emergency Medical Contacts

To ensure the safety of study participants, access to the Medical Monitors is available 24 hours per day, 7 days per week. Details will be available separately.

8.3.5 Pregnancy

POCBP will be instructed to immediately inform the Investigator if they become pregnant during the study or within 24 weeks after the final dose of study treatment, whichever is longer.

Male participants will be instructed through the ICF to immediately inform the Investigator if their partner becomes pregnant during the study or within 24 weeks after the final dose of study treatment.

If a pregnancy is reported, the Investigator should inform the Sponsor within 24 hours of learning of the pregnancy and follow up via the pregnancy reporting process as detailed in [Appendix 5](#). All pregnancies reported during the study should be followed up until there is a pregnancy outcome, with follow-up information on the infant collected according to procedures outlined in [Appendix 5](#).

Abnormal pregnancy outcomes (e.g., spontaneous abortion, fetal death, stillbirth, congenital anomalies, and ectopic pregnancy) are considered SAEs ([Appendix 5](#)).

8.3.6 Adverse Events of Special Interest

AESI are required to be reported by the Investigator to the Sponsor immediately (i.e., no more than 24 hours after learning of the event; see [Appendix 2](#) for reporting instructions).

AESI for this study include the following:

- Cases of an elevated ALT or AST value in combination with either an elevated bilirubin value or clinical jaundice, as defined in [Appendix 3](#).
- Suspected transmission of an infectious agent by the study treatment, defined as:

Any organism, virus, or infectious particle (e.g., prion protein transmitting transmissible spongiform encephalopathy), pathogenic or non-pathogenic, is considered an infectious agent. A transmission of an infectious agent may be suspected from clinical symptoms or laboratory findings that indicate an infection in a participant exposed to a medicinal product. This term applies only when a contamination of the study treatment is suspected.

8.3.7 Management of Specific Adverse Events

Injection-site reactions or hypersensitivity reactions will be managed at the Principal Investigator's discretion with appropriate documentation that the treatment course was in reaction to evident findings (i.e., acetaminophen administered in response to documented fever or pain, graded use of antihistamine, glucocorticoids, or epinephrine for appropriately severe allergic findings, meperidine administered for documented rigors). If the participant experiences any suspected HBsAg-HBsAb immune complex mediated AEs (e.g., serum sickness; please refer to the [RO7565020 IB](#) for more information), an unscheduled sample will be collected (see [Table 9](#)), and the participant will be managed according to institutional practice at the Principal Investigator's discretion. No prophylactic treatments that could mask clinical findings that may emerge upon dosing with study drug will be administered without prior consultation with the Sponsor's Medical Monitor. If a study drug-related anaphylactic or serious hypersensitivity reaction occurs, administration of RO7565020 should be stopped immediately and permanently discontinued.

In the case of a possible event of ALT elevation or virological breakthrough during study treatment in Parts 2 and 3 in participants with CHB, please consider the following recommended guidelines for management of specific AEs ([Table 9](#)).

Table 9 Guidelines for Managing Specific Adverse Events

| Event | Action to Be Taken |
|--|---|
| Injection-site reaction | 
Manage according to institutional practice. |
| Infusion-related reaction | 
If the severity of the event is Grade ≥ 2, collect unscheduled safety samples including ADA, complement activation, CRP, hematology, blood chemistry, and coagulation. |
| Hypersensitivity reactions | |
| Study drug-related anaphylactic or serious hypersensitivity reaction | 
Stop administration of RO7565020 immediately and permanently discontinue RO7565020.Manage according to institutional practice.Collect unscheduled safety samples including ADA, complement activation, CRP, hematology, blood chemistry, and coagulation. |
| For Parts 2 and 3 only (participants with CHB) | |
| Suspected HBsAg-HBsAb immune complex mediated AEs (e.g., serum sickness) | 
Manage according to institutional practice.Collect unscheduled safety samples including ADA, complement activation, CRP, hematology, blood chemistry, and coagulation. |

Table 9 Guidelines for Managing Specific Adverse Events (cont.)

| Event | Action to Be Taken |
|---|---|
| For Parts 2 and 3 only (participants with CHB) (cont.) | |
| ALT elevations during treatment: | 
 • If ALT elevation with preserved hepatic function (e.g., no significant changes in bilirubin, INR, PT, albumin, and/or ALP): 
 ○ ALT 3–10×ULN: Repeat ALT, LFTs (total bilirubin, direct bilirubin, AST, ALP, albumin), coagulation (INR, PT), and PD parameters (HBV DNA, HBsAg) every week until ALT < 3×ULN. ○ ALT > 10×ULN: Interrupt RO7565020 (in Part 3), and continue NUC treatment. Repeat ALT, LFTs, coagulation, and PD parameters twice weekly until ALT level < 10×ULN, then weekly until ALT < 3×ULN. Consider re-introducing RO7565020 on a case-by-case basis based on subsequent laboratory results. • If ALT elevation accompanied by declining liver synthetic and excretory functions (total bilirubin > 2×ULN, or albumin < 3.0 g/dL, or INR > 1.5) or other signs of hepatic impairment (severe fatigue, vomiting): 
 ○ Discontinue RO7565020 (in Part 3), and continue NUC treatment. ○ Repeat ALT, LFTs, coagulation, and PD parameters twice weekly until levels return towards baseline levels or normal range. ○ Investigate the participant for potential etiologies of the laboratory changes. ○ If alternative reasons/diagnoses cannot explain the laboratory changes, potential DILI will be considered. 
Notes:
 
 ○ Frequency of monitoring may need to be adjusted on the basis of clinical scenario and severity of injury. ○ As the central laboratory results generation and reporting will take time, additional local laboratory tests may be performed at the same time as the central laboratory test, and decision-making may be based on local laboratory results. ○ For marked and/or persistent ALT elevations, collect a spare serum sample (to allow retrospective evaluation of potential etiologies) and consider liver biopsy on a case-by-case basis (if deemed clinically relevant). • If ALT elevations are associated with increased HBV DNA levels, virological breakthrough will be suspected and managed as described below. |

Table 9 Guidelines for Managing Specific Adverse Events (cont.)

| Event | Action to Be Taken |
|---|--|
| For Parts 2 and 3 only (participants with CHB) (cont.) | |
| Virological breakthrough | 
• Participants with suspected virological breakthrough (HBV DNA > 100 IU/mL or > 1 log increase from nadir) during treatment will attend a study visit (scheduled or unscheduled) within 2 weeks for:
○ a confirmatory testing that HBV DNA > 100 IU/mL○ testing of plasma drug levels of the NUC, and serum levels of RO7565020○ collection of an additional sample for potential resistance testing, and○ thorough evaluation of compliance and factors that may be affecting treatment compliance• If virological breakthrough is confirmed:
○ The additional sample will be further tested for HBV genome characterization through HBV DNA and/or HBV RNA sequencing and where feasible phenotyping○ The Investigator will manage the CHB participant's NUC treatment, according to current guidelines and local regulations (guided by participant's treatment history, assessment of compliance, HBV DNA levels, and any available result of drug resistance testing). Blood sample for NUC PK will be collected to confirm the NUC treatment compliance○ Consider whether the study treatment RO7565020 can be continued (for Part 3 only) |

Abbreviations: ADA = anti-drug antibody; AE = adverse event; ALP = alkaline phosphatase; ALT = alanine transaminase; AST = aspartate transaminase; CHB = chronic hepatitis B; CRP = C-reactive protein; DILI = drug-induced liver injury; DNA = deoxyribonucleic acid; HBsAb = hepatitis B antibody; HBsAg = hepatitis B surface antigen; HBV = hepatitis B virus; INR = international normalized ratio; LFT = liver function test; NUC = nucleos(t)ide analogue; PD = pharmacodynamic; PT = prothrombin time; RNA = ribonucleic acid; ULN = upper limit of normal.

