6.7 TREATMENT AFTER THE END OF THE STUDY

Currently, the Sponsor does not intend to provide RO7565020 or NUC to participants after conclusion of the study or any earlier participant withdrawal.

The Sponsor will evaluate whether to continue to provide RO7565020 or NUC to participants after the main study is over, in accordance with the Roche Global Policy on Continued Access to Investigational Medicinal Product, available at the following website:

http://www.roche.com/policy_continued_access_to_investigational_medicines.pdf

7. **DISCONTINUATION OF STUDY, STUDY TREATMENT, AND PARTICIPANT DISCONTINUATION/WITHDRAWAL**

An excessive rate of participant withdrawals (either participants discontinuing study treatment or withdrawing from the study) can render the study non-interpretable. Therefore, unnecessary withdrawal of participants should be avoided and efforts should be taken to motivate participants to comply with all the study-specific procedures as outlined in this protocol.

Details on study and site closures are provided in [Appendix 1](#), Section 4.

7.1 **DISCONTINUATION OF STUDY TREATMENT**

Reasons for discontinuation of study treatment RO7565020 may include, but are not limited to, the following:

- Participant withdrawal of consent at any time.
- Any medical condition that the Investigator or Sponsor determines may jeopardize the participant's safety if he or she continues in the study.
- Investigator or Sponsor determination that treatment discontinuation is in the best interest of the participant.
- Pregnancy.
- Any other event that meets individual stopping criteria defined in Section [4.1.1.3.2](#).
- Safety and tolerability issues, e.g., acute reactions, not tolerable and not manageable with symptomatic treatment.

For Parts 2 and 3 only:

- Disease progression, e.g., any sign of development of liver cirrhosis (or liver imaging indicating cirrhosis), decompensation (e.g., ascites, variceal hemorrhage, Child-Pugh Class B or C clinical classification), or HCC
- Grade 4 ALT abnormal (i.e., $\geq 10 \times \text{ULN}$) as defined by the DAIDS Table for Grading the Severity of Adult and Pediatric Adverse Events (DAIDS AE grading table) confirmed within 48 to 72 hours
- Grade 3 ALT abnormal (i.e., $> 5 \times \text{to} < 10 \times \text{ULN}$) combined with total bilirubin $> 2 \times \text{ULN}$ (of which $> 35\%$ is direct bilirubin), or Grade 3 ALT abnormal and INR > 1.5

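### For optional Part 3, Section 7.1 and Table 9 prescribe different actions for confirmed ALT of 10 × ULN or more with preserved hepatic function, and no text says which governs.

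*Combined protocol and SAP*

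**What the plan says.** Section 7.1 opens its list with "Reasons for discontinuation of study treatment RO7565020 may include, but are not limited to, the following". For Parts 2 and 3 it then names two ALT criteria:

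- Grade 4 ALT, given as at least 10 × ULN, "confirmed within 48 to 72 hours". No condition on hepatic function is attached.
- Grade 3 ALT (above 5 and below 10 × ULN) with total bilirubin above 2 × ULN, more than 35% of it direct, "or Grade 3 ALT abnormal and INR > 1.5".

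Table 9 in Section 8.3.7 is introduced as recommended guidance for investigators to consider. It divides ALT elevations by hepatic function:

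- Preserved function, lower band: "ALT 3–10×ULN: Repeat ALT, LFTs", with coagulation and PD parameters, every week.
- Preserved function, upper band: "ALT > 10×ULN: Interrupt RO7565020 (in Part 3), and continue NUC treatment". After closer monitoring it adds "Consider re-introducing RO7565020 on a case-by-case basis based on subsequent laboratory results".
- Impaired function: "If ALT elevation accompanied by declining liver synthetic and excretory functions (total bilirubin > 2×ULN, or albumin < 3.0 g/dL, or INR > 1.5". Symptoms such as severe fatigue or vomiting also qualify. The action is to discontinue RO7565020 in Part 3.

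Section 6.6.1 asks that interruption be considered before permanent discontinuation, and that interrupted participants restart once the investigator finds it medically justified. Section 6.1 points to 6.6.1 for interruption and to Section 7 for discontinuation. The ALT text in 7.1 and the ALT row of Table 9 do not refer to each other.

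**The concern.** A Part 3 participant with confirmed ALT above 10 × ULN and otherwise normal liver tests meets a listed discontinuation criterion in one section. In the other, the same participant is a candidate for further dosing. The protocol treats interruption and discontinuation as separate actions with separate consequences. Under Section 7.1, a participant who discontinues early is asked back for a completion or early termination visit, and one who stops for safety reasons is not replaced. An interrupted participant is expected to restart when justified.

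Two things are at stake. One is a liver stopping criterion in a first-in-human study whose benefit–risk section relies on pre-specified stopping criteria. The other is a primary endpoint component, treatment discontinuations due to AEs. Appendix 3, Section 9 says abnormal liver function tests under Section 8.3.7 are reported as AEs. The same laboratory course could therefore be an AE with interruption or an AE leading to discontinuation, depending on the text applied.

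**Working it through.** The plan gives no figure on this point to reproduce. The check applies both sets of criteria, as written, to the same laboratory pictures. Inputs are the ALT criteria in Section 7.1 and the ALT row of Table 9.

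Assumptions: Grade 4 values are confirmed within the window; any ALT above normal counts as an elevation for Table 9's impaired-function row, which states no multiple; the participant is in Part 3.

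**Preserved function**

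| ALT (× ULN) | Section 7.1 | Table 9 |
|---|---|---|
| 4, 6, 9.9 | not listed | weekly tests |
| 10 | discontinuation listed | weekly tests |
| 12 | discontinuation listed | interrupt, consider re-introduction |

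The sections part at 10 and at 12. The difference at exactly 10 arises because 7.1 uses at least 10, while Table 9 puts 10 in its lower band and starts the upper band above it.

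**Impaired function**

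| Picture | Section 7.1 | Table 9 |
|---|---|---|
| ALT 6, bilirubin 2.5 × ULN, 50% direct | discontinuation listed | discontinue |
| ALT 6, INR 1.6 | discontinuation listed | discontinue |
| ALT 10 or 12, any impairment | discontinuation listed | discontinue |
| ALT 6, bilirubin 2.5 × ULN, 20% direct | not listed | discontinue |
| ALT 6, albumin 2.8 g/dL | not listed | discontinue |
| ALT 4, INR 1.6 | not listed | discontinue |

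Every combined trigger in 7.1 also leads to discontinuation in Table 9. The reverse is not true: 7.1 has a Grade 3 ALT floor and a direct-bilirubin share, while Table 9 has neither and adds albumin and symptoms. Because the 7.1 list is open-ended, not listed does not mean continue dosing.

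**A third text.** Section 4.1.1.3.2, which 7.1 cites, discontinues a multiple-dose participant for a severe (Grade 3) reaction judged related to RO7565020. For ALT above 5 and below 10 × ULN with preserved function, Table 9 gives monitoring only and makes no exception for related events.

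**Size.** Section 9.2 plans 6 participants per Part 3 cohort and at most 2 cohorts:

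- one participant in a cohort: 1/6 = 16.7 percentage points;
- one participant across both cohorts: 1/(2 × 6) = 1/12 = 8.3 percentage points.

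These are the effects of reclassifying one participant. The documents give no expected frequency for these pictures, and none is assumed.

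**The case against.** The strongest reply is that neither text is a binding rule. Section 7.1 offers reasons that may apply, Table 9 is guidance, and 6.6.1 puts interruption first. The texts can also be read in sequence: interrupt when ALT passes 10 × ULN, then apply 7.1 once the value is confirmed. Decisions are not left to the site alone: Section 8 has immediate safety concerns discussed with the sponsor, and Section 4.1.1.4 requires immediate contact for a severe AE. Part 3 is optional and small, and no hypothesis is tested.

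Much of this stands, and it rules out three stronger readings that a reader might infer:

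- That 7.1 imposes a permanent stop. The ALT criteria do not say so, whereas the anaphylaxis text in Section 8.3.7 does use the word permanently.
- That the impaired-function criteria contradict each other. They are unequal triggers: Table 9 contains those in 7.1, and 7.1 leaves room for more, including the investigator's or sponsor's judgement of the participant's best interest.
- That sites would necessarily stop different participants. Contact with the sponsor limits that, although the sponsor would be working from the same two texts.

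The reply does not remove the main point. Two non-binding texts with different actions leave the action undetermined. The sequential reading fails because Table 9 does not restrict re-introduction to unconfirmed values. Section 6.6.1 says that interruption comes up for consideration first; it does not say whether someone who has met a listed 7.1 criterion may be dosed again.

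**Conclusion.** The point holds for confirmed ALT of 10 × ULN or more with preserved hepatic function in Part 3. Section 7.1 lists discontinuation; Table 9 gives interruption with possible re-introduction above 10 × ULN and weekly monitoring at exactly 10. No text gives precedence. The mismatch in impaired-function triggers is secondary: it calls for alignment but is not a conflict of instructions.

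The reach is limited to Part 3, at most 12 planned participants. Parts 2a and 2b are single-dose, so there is no later dose to stop. Exposure differs only if dosing is in fact resumed; the count of discontinuations can differ even if it is not. No sample-size figure depends on the point. The conclusion assumes that interruption and discontinuation are distinct actions, as Sections 6.1 and 6.6.1 imply.

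**What to change.** Before Part 3 opens, the sponsor should:

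- reconcile Sections 6.6.1 and 7.1 with the ALT row of Table 9 for confirmed ALT of 10 × ULN or more, including the boundary at exactly 10;
- make explicit whether a participant who meets the 7.1 criterion may be dosed again;
- align the impaired-function triggers, or state that the difference is intended;
- check the result against the individual stopping rule in Section 4.1.1.3.2;
- cross-refer the sections and state which text governs.

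The thresholds and the re-introduction policy are the sponsor's choice, and this review takes no position on them. The cost is protocol wording only. ALT, bilirubin with its direct fraction, albumin and INR are already in the Appendix 4 laboratory panel, so no tests or visits are added.
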